It is well known that the use of charcoal CNS is usually performed during surgery, but in our medical center, we found that preoperative injection of carbon nanoparticles by fine needle aspiration under ultrasound guidance can have better results by reducing CNS leakage in the surgical area. Possible reasons for this include:

- (i) preoperative ultrasound-guided intra-glandular lobe injection of carbon

nanoparticles does not have to open the surgical peritoneum of the thyroid gland, which reduces possible lymphatic vessel damage and makes lymphatic drainage more consistent with normal physiology; (ii) preoperative injection allows for a more adequate time for lymphatic dispersion of the carbon nanoparticles; and (iii) preoperative labeling of suspected metastatic lymph nodes by carbon nanoparticles injection further improves the tracing effect of the lymph nodes.

II.Purpose of the study

The purpose of this study was to investigate the effect of carbon nanoparticles injections at different preoperative and intraoperative times on surgical procedures and postoperative complications in patients with unilateral and bilateral papillary thyroid cancer or lymph node metastases.

III.Study population

One hundred and fifty patients who came to our hospital from January 2025 to June 2025, who were diagnosed with unilateral bilateral PTC or lateral LN metastasis by preoperative FNA (fine needle aspiration) or preoperative ultrasonography suggestive of TRAIDs grading 4a and above, and who were proposed to undergo laparoscopic thyroid surgery, were selected. Based on the objective conditions and subjective requirements of the patients, these patients were first divided into a partial thyroidectomy group (i.e., a unilateral lobectomy or partial thyroidectomy was performed) and a total thyroidectomy group (a total thyroidectomy was performed), and under the two groups, according to the timing of carbon nanoparticles injections, they were divided into two subgroups: a preoperative subgroup and a suboperative subgroup. In the preoperative subgroup, carbon nanoparticles was injected into the thyroid gland 2-6 hours prior to surgery, whereas in the suboperative subgroup, carbon nanoparticles was injected intraoperatively.

Inclusion Criteria:

- (1).Preoperative pathological assessment indicated the presence of thyroid cancer

with a maximum diameter of less than 4 cm.

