(2). Postoperative pathological evaluation confirmed bilateral thyroid cancer or lateral lymph node metastasis.

(3). Vocal cord examination conducted one week prior to surgery revealed no abnormalities.

(4). The patient had no history of prior thyroid surgery and required a total thyroidectomy.

(5). Blood pressure was stably controlled.

(6). The patient regained consciousness and was able to communicate normally.

Exclusion criteria

(1) Prior to enrollment, the patient had received radiotherapy, chemotherapy, or isotope therapy;

(2) A documented history of thyroid surgery;

(3) Age under 16 years;

(4) Known allergies to the medications under investigation or an inability to tolerate surgical intervention;

(5) Presence of a retrosternal thyroid tumor;

(6) Tumor invasion of the parathyroid glands and/or the recurrent laryngeal nerve during surgical procedures;

(7) Postoperative pathology suggestive of medullary carcinoma or undifferentiated carcinoma;

(8) Development of a postoperative tracheal fistula.

IV. Observation indicators

(1). General information: age; gender; height; weight; BMI; tumor size; tumor location; pathology results; preoperative serum calcium; preoperative thyroid hormone;

(2). Preoperative parathyroid hormone levels; preoperative TSH; preoperative vocal cord movement problems.

(3). Carbon nanoparticles injections: carbon nanoparticles injection site; number of carbon nanoparticles injection needles; carbon nanoparticles injection dose.

(4). Carbon nanoparticles staining: thyroid staining; lymph node staining; parathyroid staining; nanocarbon leakage.

(5). Intraoperative data: length of surgery, number of lymph nodes cleared, amount of intraoperative bleeding.

(6). Postoperative data: postoperative pain duration; postoperative drainage; postoperative hospitalization; postoperative serum parathyroid hormone; postoperative laryngeal recurrent nerve stimulation and injury; postoperative hematoma; postoperative tracheal fistula.

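### Postoperative tracheal fistula is both a reason for exclusion and a listed postoperative outcome, so its rate among analysed patients is 0 in every group by construction

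*Protocol*

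**What the plan says.** The last exclusion criterion in section III of the protocol, number (8), is "Development of a postoperative tracheal fistula".

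Section IV(6), the list of postoperative data, ends with "postoperative hematoma; postoperative tracheal fistula". The same list includes "postoperative drainage; postoperative hospitalization; postoperative serum parathyroid hormone; postoperative laryngeal recurrent nerve stimulation and injury".

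Section II says the study looks at the effect of injection timing "on surgical procedures and postoperative complications".

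Section III fixes when the injection is given. In the preoperative subgroup it is "injected into the thyroid gland 2-6 hours prior to surgery, whereas in the suboperative subgroup, carbon nanoparticles was injected intraoperatively".

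On numbers, section III says only "One hundred and fifty patients who came to our hospital", described as patients "who were proposed to undergo laparoscopic thyroid surgery, were selected". It gives no group sizes and no expected fistula rate.

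**The concern.** An exclusion criterion should normally be decidable before treatment. Criterion (8) is not: a postoperative fistula can only appear after the injection and the operation. It therefore removes treated patients because they had a complication, in a study whose purpose includes comparing complications.

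Two things are at stake. First, the fistula result cannot be interpreted, because a reader cannot tell a true zero from an imposed one. Second, a patient removed under (8) also takes their other section IV(6) results out of the analysis: drainage, hospital stay, parathyroid hormone and nerve injury. The protocol does not say that collection of these data stops, only that the patient is excluded.

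**Working it through.** **Step 1. Order of events.** Injection (2-6 hours before surgery, or during it) comes first, then the end of surgery, then any postoperative fistula. Criterion (8) therefore always acts after the exposure being compared, in both timing subgroups and in both the partial and total thyroidectomy groups.

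**Step 2. Effect on the fistula rate.** The protocol states no fistula rate, so there is no figure of its own to reproduce. Let p be the true rate in a group, with p below 1. Once (8) is applied:

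P(fistula | retained) = P(fistula and no fistula) / P(no fistula) = 0 / (1 − p) = 0.

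This holds for any p in every group, so the observed difference between groups is also 0 whatever the true difference. The step needs no outside figure.

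**Step 3. How many patients might be affected (illustration only).** Inputs:

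- N = 150 treated. This is an assumption: section III says 150 were selected, not how many are treated. The range 120 to 180 is shown as well.
- p = 0.1%, 0.5%, 1% and 2%. These are assumptions with no source in the protocol.

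Formulas: expected exclusions under (8) = N × p; chance of at least one = 1 − (1 − p)^N. For example, at N = 150 and p = 1%: 150 × 0.01 = 1.5, and 1 − 0.99^150 = 0.779.

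| Assumed p | Expected exclusions, N = 150 | Chance of at least one, N = 150 | N = 120 | N = 180 |
|---|---|---|---|---|
| 0.1% | 0.15 | 0.139 | 0.113 | 0.165 |
| 0.5% | 0.75 | 0.529 | 0.452 | 0.594 |
| 1% | 1.5 | 0.779 | 0.701 | 0.836 |
| 2% | 3 | 0.952 | 0.911 | 0.974 |

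**Step 4. What cannot be computed.** The number analysed cannot be derived, because other criteria also remove operated patients: inclusion (2), "Postoperative pathological evaluation confirmed bilateral thyroid cancer or lateral lymph node metastasis", and exclusions (6) and (7), which depend on findings at surgery and on postoperative pathology. No per-group figure is possible, because no group sizes are stated.

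**Step 5. Limits of the damage.** Criterion (8) does not remove patients with hematoma, nerve injury or low parathyroid hormone unless they also have a fistula. The comparison of those outcomes is biased only if fistula occurs at different rates in the timing groups, and the protocol gives no evidence either way.

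**The case against.** The strongest counter-argument has four parts.

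- **Fistula is a minor item.** It is one of seven entries in section IV(6). The Background discusses only hypoparathyroidism and recurrent laryngeal nerve injury as complications, and fistula appears nowhere outside (8) and IV(6). At an assumed rate of 0.1%, there is only a 14% chance that even one of 150 patients is affected. This stands as a limit on the number of patients involved. It does not remove the conflict, and the protocol gives no rate from which rarity could be argued.
- **Section IV may record fistula only in order to apply (8).** That section does list other items that bear on eligibility: vocal cord movement, which inclusion (3) also covers, and pathology results, which decide inclusion (2) and exclusion (7). The reading is possible, but the protocol does not state it, and the entry sits beside hematoma and nerve injury, which are outcomes. Even on this reading the rate among retained patients is 0.
- **A statistical analysis plan, not available here, may define a wider set for complications.** It may, and the absence of an analysis set from the protocol is not the complaint. The complaint is that two items of the protocol conflict, and the eligibility text would still need correcting.
- **Deletion is not the only remedy.** Keeping (8) for other comparisons while reporting fistula for all treated patients would also remove the uninformative zero. That is true of the fistula rate, but those patients' other outcomes would still be dropped because of a complication.

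**Conclusion.** The point holds and must be fixed. What is certain from the protocol text alone is that, with criterion (8) applied as written, the fistula rate among analysed patients is 0 in every group, whatever the truth.

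The number of patients lost is not known. At assumed rates of 0.1% to 2% it is 0.15 to 3 expected cases among an assumed 150 treated, so the practical effect could be nil or a few patients. Bias in the timing comparison of other outcomes is conditional on unequal fistula rates and is not shown. The severity rests on the kind of error, which is removing treated patients for a complication listed for observation, and not on a large expected count.

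**What to change.** Delete exclusion (8), so that no patient is removed because of a fistula, and report fistula by injection-timing group under section IV(6).

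Deletion alone does not give an all-treated denominator, because inclusion (2) and exclusions (6) and (7) still remove operated patients. If that denominator is wanted, add one sentence: tracheal fistula is reported for every patient who received the injection and surgery, including those removed from other analyses by inclusion (2) or exclusions (6) and (7).

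The cost is a one-line deletion and, if wanted, one reporting sentence. No new data are needed, since section IV(6) already lists the item. The reported complication rate may look slightly less favourable.

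### No indicator in section IV records adverse events of the preoperative injection before surgery starts, so injection harms are ascertained unequally in the two subgroups

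*Protocol*

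**What the plan says.** Section III of the Protocol sets the contrast. For the first arm it states: "In the preoperative subgroup, carbon nanoparticles was injected into the thyroid gland 2-6 hours prior to surgery". The comparator, by contrast, receives the injection while the operation is under way. Section I.3 describes the preoperative technique as "preoperative injection of carbon nanoparticles by fine needle aspiration under ultrasound guidance", so it is a needle procedure separate from the operation.

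Section IV has six groups of indicators. Item (3), on the injection, reads "Carbon nanoparticles injections: carbon nanoparticles injection site; number of carbon nanoparticles injection needles; carbon nanoparticles injection dose". Item (4), on staining, lists "thyroid staining; lymph node staining; parathyroid staining; nanocarbon leakage". Item (5), on the operation, lists "length of surgery, number of lymph nodes cleared, amount of intraoperative bleeding". Item (6) is headed as postoperative data. It covers pain duration, drainage, hospital stay, parathyroid hormone and recurrent laryngeal nerve injury, and ends with "postoperative hematoma; postoperative tracheal fistula". Items (1) and (2) are patient, tumour and preoperative characteristics.

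Inclusion criterion (2) in section III requires confirmation by postoperative pathology. The document shown has no general collection of adverse events.

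**The concern.** The preoperative strategy adds a needle procedure and a wait of 2-6 hours that the comparator does not have. A complication arising in that wait belongs to the strategy under test, yet the indicator list has no place for it. The comparator's injection takes place inside the operation, where at least bleeding is measured. The same kind of event can therefore be counted in one subgroup and missed in the other.

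What is at stake is the fairness of the harm comparison and the chance of noticing a safety signal. Section I.3 itself says that preoperative injection lacks a complete guideline and that its timing, dose and method are not standardised. Its remark that no allergic reactions occurred follows a sentence about intraoperative injection, and section IV has no allergy item that could test the remark here. What is observed, and from when, is fixed when data are collected. An analysis plan cannot recover events that were never recorded.

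**Working it through.** The Protocol states no figure on this point, so there is nothing to reproduce. The main check is a comparison of the indicator list with the two injection schedules.

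**Step 1. Which item could hold an injection-related event?**

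| Event | Preoperative subgroup, between injection and incision | Intraoperative subgroup, at or after injection during surgery |
|---|---|---|
| Neck bleeding | No item | Item (5), amount of intraoperative bleeding |
| Haematoma | No item, unless still present after surgery (item 6) | Item (6) if present after surgery |
| Allergic reaction | No item | No item |
| Airway symptoms | No item | No item |
| Injection pain | No item; item (6) has only the duration of postoperative pain | Not comparable, since the injection is given during surgery |
| Surgery delayed or cancelled | No item | Cannot follow from an injection given during surgery |
| Leakage, parathyroid staining | Item (4) | Item (4) |

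The table shows two kinds of gap. Bleeding is ascertained unequally: it is measurable in the comparator and not in the preoperative window. Allergic reaction and airway symptoms have no item in either subgroup. Leakage and staining are covered equally.

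**Step 2. What happens to a patient injected but not operated on?** Inclusion criterion (2) depends on postoperative pathology. Without an operation there is none, so the criterion cannot be met and the patient leaves the study population. Only the preoperative subgroup has an interval between injection and surgery in which this can happen. An injection event serious enough to stop the operation would remove its own record.

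**Step 3. Illustration of what recording would yield.** Section III gives 150 patients in total and no allocation ratio. Assumptions: n = 75 in the preoperative subgroup (150/2), varied from 50 to 100, and a true event rate p of 1% to 5%. Neither p nor n comes from the documents.

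Chance of at least one event = 1 − (1 − p)^n:

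- n = 75: 1 − 0.99^75 = 0.529; 1 − 0.95^75 = 0.979
- n = 50: 1 − 0.99^50 = 0.395; 1 − 0.95^50 = 0.923
- n = 100: 1 − 0.99^100 = 0.634; 1 − 0.95^100 = 0.994

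If events were recorded and none occurred, the exact two-sided 95% upper limit is 1 − 0.025^(1/n). For n = 75 this is 1 − 0.025^(1/75) = 0.048, or 4.8%. The one-sided 95% limit, 1 − 0.05^(1/75), is 3.9%. These are two conventions and do not conflict.

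**The case against.** The strongest reply is that the indicators match the stated purpose in section II, which is the effect on surgical procedures and postoperative complications. No sentence of the Protocol is contradicted, and adverse-event reporting may sit in safety material that is not shown. It is true that nothing is contradicted, and the second point is possible. However, a comparison of two injection times should count the harms of both injections over periods that start at the injection, and the list shown does not do so.

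A reader might infer that the trial counts only the benefits of preoperative injection and none of its risks. The documents do not support that. Leakage and parathyroid staining are recorded, and section I.3 treats leakage as a threat to recognition of the parathyroid glands. Intraoperative bleeding, pain duration, parathyroid hormone, nerve injury and haematoma are also listed, none of them for one subgroup only. Nor are all the complication items restricted to the postoperative period: leakage, staining and intraoperative bleeding are not.

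A reader might also infer that no needle complication would ever appear in the data. That too goes beyond the text. A nerve injury, or bleeding that persists into surgery, could surface in items (5) or (6). It could not then be told apart from surgical harm. What is lost outright is mainly transient pain, allergic reaction, airway symptoms, self-limiting bleeding, and delay or cancellation.

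Finally, adding boxes to item (3) would not be enough, because a patient whose operation is cancelled fails inclusion criterion (2). That objection is right, and the fix has to address it.

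**Conclusion.** The point holds in a limited form. Section IV has no indicator for adverse events between the preoperative injection and the start of surgery. Bleeding from an intraoperative injection can be caught, so harms are ascertained unequally. If such events occur, the omission understates the harms of preoperative injection.

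How far it does so cannot be derived from the documents. It is tempting to say that the 2-6 hour wait is where the two strategies differ most in risk, but the Protocol gives no risk for that interval. The figures of 53%-98% at 75 patients (39.5%-92.3% at 50, 63.4%-99.4% at 100) follow from assumed rates and arm sizes. They show that at least one event could plausibly occur, and they are not evidence of bias. Even the modest reassurance of an upper limit of 4.8% after no events in 75 patients would be available only if the events were recorded. This is a cheap improvement that is relevant to safety and should be made; it does not invalidate the design.

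**What to change.** 1. Add to section IV an item for injection-related events: neck bleeding or haematoma, allergic reaction, airway symptoms, and surgery delayed or cancelled. Use the same definitions in both subgroups and count from the time of injection.
2. Record injection pain descriptively in the preoperative subgroup only. The comparator is injected during surgery, so a like-for-like comparison is not possible.
3. Report all injected patients for safety, by subgroup, including any who were not operated on and so cannot meet inclusion criterion (2).
4. State that the observation period before incision differs between the subgroups by the 2-6 hour wait, so that the event counts are read with that in mind.

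The cost is a few more fields on the case form, an added item in section IV and a separate safety count. Only data collection and reporting change; treatment does not.
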